### 11.4.2 ANALYSIS OF THE SECONDARY ENDPOINT(S)

#### 11.4.2.1 *Rate of serious adverse event*

Using the safety analysis set, the incidence of serious adverse events following endoscopic BTX injection into the sphincter of Oddi as a single agent will be determined for participants undergoing distal pancreas resections. The 95% confidence interval will be reported with the point estimate of SAE rate.

#### 11.4.2.2 *Rate of any POPF*

Using the efficacy analysis set, the estimate of biochemically or clinically relevant POPF rate on pre-operative endoscopic BTX injection will be measured and reported with 95% exact confidence interval.

### 11.4.3 ANALYSIS OF THE EXPLORATORY ENDPOINT(S)

Exploratory analysis will be performed with historical patients accounting for the covariates that predict experiencing a crPOPF. That is, to estimate the effect of pre-operative endoscopic BTX injection on crPOPF for this non-randomized trial, we will use disease risk score matching to pair treatment and control units with similar values on the disease riskscore with known risk factors for crPOPF with the following endpoints of interest at 30 days postoperatively. The disease risk score model will be derived from the historical control cohort, which consists of distal pancreas resections from 2013-2020 with pancreas-specific National Surgical Quality Improvement Program (NSQIP) information. The historical control group has experienced approximately 30 crPOPFs, which is sufficient for estimation of crPOPF risk using the predictive variables captured by NSQIP and supplemental chart review. Individual patients from the historical and intervention groups will be assigned disease risk scores, and matched according to scores.

As data allow, the benefit of pre-operative BTX injection for 30 days outcomes will be analyzed using disease risk score matching using known risk factors for crPOPF against historical patient controls for the following endpoints :

- 1) Clinically relevant POPF
- 2) Any POPF
- 3) Postoperative Length of Stay
- 4) Clavien-Dindo III or greater postoperative complications
- 5) Rate of percutaneous drainage procedure
- 6) Rate of unplanned re-operation

#### 11.4.4 SAFETY ANALYSES

Adverse events will be tabulated by the Medical Dictionary for Regulatory Activities (MedDRA Version 21.1) preferred term and system organ class. The severity of the AE will be assessed by National Cancer Institute (NCI) Common Terminology Criteria for Adverse Events (CTCAE) version 5.0. Using the safety analysis set, descriptive statistics will be used to summarize all on-study AEs, grade 3-4 AEs, treatment-related AEs, grade 3-4 treatment-related AEs, SAEs, treatment-related SAEs, and AEs leading to study therapy discontinuation. Grade 3-4 laboratory abnormalities will be summarized using worst grade NCI CTCAE v5.0 criteria.

#### 11.4.5 PLANNED INTERIM ANALYSES AND STOPPING RULE

A safety-run in to test the endoscopic BTX injection technique will be performed. During the safety run-in, the PI will evaluate patient safety outcomes including grade 3 or higher adverse events. Additionally, the study will be evaluated by the DSMC following the completion of the first three participant's safety evaluation periods (30 days following BTX injection or 30 days following surgery, whichever is longer). Progressive study enrollment will continue throughout the safety run-in, and enrollment will be halted if recommended by the DSMC after completion of the run-in. If 2 or more of the first 6 participants enrolled experience delay in planned surgery  $\geq$  14 days (due to significant GI hemorrhage, perforation, or adverse reaction to BTX) or pancreatitis requiring hospitalization, then the study will be halted for safety. If 2 or more of the first 6 participants experience delay in planned surgery  $\geq$  14 days (due to significant GI hemorrhage, perforation, or adverse reaction to BTX) or pancreatitis requiring hospitalization, the study will be halted for safety. An analysis of adverse events will be performed, and if an alteration in the intervention technique or other prophylactic treatment cannot be identified the study will be terminated. If an alteration or prophylactic treatment can be found, the study will resume with an additional 6 patient safety run-in with identical stopping rules.

A futility analysis will be conducted based on the stopping rule of Simon's two-stage design after 25 Stage I participants have met the eligibility criteria for the efficacy evaluable population (defined in 11.3.2). All participants enrolled on stage 1 (n=25) will need to complete the study intervention, distal pancreas resection, and 30 days of follow up for postoperative pancreatic fistula before the interim analysis can be completed. Recruitment will be paused until interim analysis is completed. The trial will be terminated if there are 2 or more crPOPF among these 25 participants. If there are less than 2 crCOPF among these Stage I participants, the trial will continue and enroll 25 additional participants in Stage II. The treatment will be considered promising and deserving of further investigation if there are less than 3 crCOPF among the total of evaluable 50 participants.

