	Preoperative endoscopy with Sphincter of Oddi BTX injection will be the only trial-related intervention for patients participating in this trial. All the other procedures, including assessment of laboratory parameters, belong to the standard perioperative and postoperative procedures performed in patients undergoing distal pancreatectomy. In patients with childbearing potential, a pregnancy test will be performed during the routine preoperative laboratory examinations.
Statistical Analyses	This is a single arm, open-label, Phase II study to estimate the rate of clinically relevant POPF in participants that receive pre-operative endoscopic BTX injection. Using a Simon's 2-stage, a total of 50 evaluable participants will achieve an 88% power to detect a difference in crPOPF rate of 9.2% (H0: $\pi = 0.112$ versus Ha: $\pi = 0.02$ ; with a one-sided alpha level of 0.05). The trial will be continued following stage 1 if there is one or fewer crPOPF among the first 25 participants. If the study proceeds to stage 2, a total of 50 participants will be evaluated towards the primary endpoint, and the intervention considered promising if there are two or fewer cases of crPOPF.

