### 3. STUDY DESIGN

#### 3.1 DESCRIPTION OF THE STUDY DESIGN

Refer to Section 11, *Statistical Analysis* for additional information regarding statistical methods used in this study.

This is a Phase II, open-label study to estimate the rate of crPOPF in patients that receive pre-operative endoscopic BTX injection into the sphincter of Oddi as a single agent prior to undergoing distal pancreas resections. The study design consists of a single arm intervention group (n=50) with comparison to historical rates for crPOPF. BTX injection will occur 7-14 days before the planned date of surgery as an outpatient endoscopic procedure. Thereafter, participants will receive all surgery and postoperative treatment in accordance with institutional standards.

The trial will commence with the enrollment of the first six patients for a safety-run in of the endoscopic BTX injection technique. During the safety run-in, the PI will evaluate patient safety outcomes including grade 3 or higher adverse events. Additionally, the study will be evaluated by the DSMC following the completion of the first three participant's safety evaluation periods (30 days following BTX injection or 30 days following surgery, whichever is longer).

Progressive study enrollment will continue throughout the safety run-in, and enrollment will be halted if recommended by the DSMC after completion of the run-in. If 2 or more of the first 6 participants enrolled experience delay in planned surgery  $\geq$  14 days (due to significant GI hemorrhage, perforation, or adverse reaction to BTX) or pancreatitis requiring hospitalization,

then the study will be halted for safety. A total of 25 patients will be enrolled prior to a planned interim analysis for the primary endpoint of interest (crPOPF). If sufficient number of participants have experienced crPOPF (2 or greater), the trial will be prematurely terminated. If the interim analysis does not result in study termination, enrollment of the remaining participants will resume to enroll a total of 50 patients completing study intervention and follow-up.

The study schedule will be divided into 2 periods: (1) the post-treatment period which starts at the time of BTX injection and ends on the day of surgery (2) the postoperative period which begins at the time of surgery and ends 30 days postoperatively.

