### 10.7 STUDY STOPPING RULES

The overall study will be paused, and appropriate authorities (e.g., IRB, Knight Data and Safety

Monitoring Committee) notified if the following events occur:

- Life-threatening grade 4 toxicity attributable to protocol therapy that is unmanageable, or unexpected.
- Death suspected to be related to BTX injection.
- As indicated by statistical stopping rules in this protocol per Section 11.4.5: 1) During safety run-in if two or more out of the first six participants experience a surgical delay  $\geq$  14 days past the previously scheduled date. 2) Interim analysis if two or more of the first 25 participants experience crPOPF. If either of these events are met the trial will be stopped. In the case of the safety run-in, the trial may be resumed if a correctable cause for the serious adverse events can be found or a prophylactic treatment administered.

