### 11.2 SAMPLE SIZE DETERMINATION

This will use a Simon's two-stage design. The two-stage design to test a difference of 9.2% (2% vs. 11.2%) has an expected sample size of 30.33 and a probability of early termination of 0.787. If the pre-operative BTX injection is effective, there is a 0.124 probability of concluding that it is not, equivalently 0.876 power. After the pre-operative BTX injection on 25 patients in the first stage, the trial will be terminated if 2 or more crPOPF. If the trial goes on to the second stage, a total of 50 participants will be studied. If the total number crPOPF is less than 3, the drug will be considered efficacious. Anticipating 10% drop-out (lost follow-up), up to 55 participants need to be enrolled to achieve 50 evaluable participants. The sample size and power analysis were conducted using PASS 15 software (<http://www.ncss.com/software/pass/>).

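### The plan does not say what happens if a second stage 1 crPOPF is seen before the 25th participant is injected, when the go/no-go result is already fixed

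*Combined protocol and SAP*

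**What the plan says.** The design in Section 11.2 and the Synopsis is a Simon two-stage plan: 25 participants, stop with two or more crPOPFs, otherwise continue to 50 and call the treatment promising with two or fewer in total.

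Three places fix the timing of the stage 1 decision at the end of stage 1:
- Section 11.4.5: "All participants enrolled on stage 1 (n=25) will need to complete the study intervention, distal pancreas resection, and 30 days of follow up" before the interim analysis can be finished. Recruitment is paused only for that analysis.
- Section 3.1: "A total of 25 patients will be enrolled prior to a planned interim analysis".
- Synopsis: "The trial will be continued following stage 1 if there is one or fewer crPOPF among the first 25 participants".

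Section 10.7 is worded differently. Under a lead-in about events whose occurrence pauses the study, beside related deaths and grade 4 toxicity, it lists "Interim analysis if two or more of the first 25 participants experience crPOPF", and then says that the trial stops if the condition is met. The same item points to Section 11.4.5 as its source and labels itself an interim analysis.

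No section addresses a second crPOPF that becomes known before the 25th participant has been injected.

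**The concern.** Success needs at most one crPOPF in the first 25 and at most two in 50. A second confirmed stage 1 event therefore settles the primary decision, whatever happens to later participants. If the team follows 11.4.5 to the letter, it goes on injecting up to participant 25. If it follows the event wording of 10.7, it pauses at once. The choice determines how many people are exposed.

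The endoscopy with injection is the only trial-specific procedure (Synopsis). Section 1.3.1 lists its risks: pancreatitis, hemorrhage, perforation and sedation events. Participants are also barred from other fistula prophylaxis (Sections 7.4 and 7.6), which Section 3.1 says many of the study surgeons currently use. After the second event, these burdens continue with no possible effect on the go/no-go result.

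**Working it through.** **Inputs.** Null rate 0.112 and alternative 0.02 (11.2); n1 = 25, stop at 2 or more; n = 50, success at 2 or fewer (Synopsis, 11.2, 11.4.5). For the lag check: accrual over 36 months (4.4.1); 50, 55 or 64 participants (Synopsis, 11.2); 7-14 days from injection to surgery (3.1); 30-day outcome; NSQIP lag up to three months, with chart review allowed for the interim (13.1.2.1).

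**1. Reproduce the stated design.** With X1 and X2 the crPOPF counts in each block of 25:
- At 0.112, P(X1=0) = 0.0513 and P(X1=1) = 0.1618. The probability of early termination is 1 - 0.0513 - 0.1618 = 0.787. The plan gives "a probability of early termination of 0.787".
- E[N] = 25 + 25 × (1 - 0.7868) = 30.33. The plan states: "The two-stage design to test a difference of 9.2% (2% vs. 11.2%) has an expected sample size of 30.33".
- P(success) = P(X1=0)·P(X2≤2) + P(X1=1)·P(X2≤1).
  - At 0.112: 0.0513 × 0.4581 + 0.1618 × 0.2132 = 0.0235 + 0.0345 = 0.0580.
  - At 0.02: 0.6035 × 0.9868 + 0.3079 × 0.9114 = 0.5955 + 0.2806 = 0.8761. The plan states "there is a 0.124 probability of concluding that it is not, equivalently 0.876 power".

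**2. Halt at the second stage 1 event, outcomes known at once.** Let T2 be the participant with the second crPOPF. Expected stage 1 size = E[min(T2, 25)] = sum over t = 0 to 24 of P(fewer than 2 events in t participants).
- At 0.112 this is 15.50 instead of 25, a saving of 9.50. Overall E[N] = 15.50 + 25 × 0.2132 = 20.82.
- Given that stage 1 fails, the second event falls on average at participant 12.9, so the saving is then 25 - 12.9 = 12.1.
- At 0.02 the expected stage 1 size is 24.26, a saving of 0.74.

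**3. P(success) under the halt.** Participant-by-participant enumeration gives 0.0580 and 0.8761 again. Every path that is cut short was already a failure.

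**4. Allow for outcome lag.** If L further participants are injected before the second event is known, the saving is E[max(0, 25 - T2 - L)]. Accrual is 50/36 = 1.39 to 64/36 = 1.78 per month, assumed constant. A full outcome takes 7 + 30 = 37 to 14 + 30 = 44 days, so L runs from 1.39 × 37/30.44 = 1.7 to 1.78 × 44/30.44 = 2.6. A further 90 days for NSQIP (134 days) gives L of 6.1 to 7.8.

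| Lag (participants) | Saving at 11.2% | E[N] at 11.2% | Saving at 2% |
|---|---|---|---|
| 0 | 9.5 | 20.8 | 0.7 |
| 2 | 8.0 | 22.3 | 0.6 |
| 3 | 7.3 | 23.1 | 0.5 |
| 6.1 to 7.8 | 5.2 to 4.2 | 25.1 to 26.2 | 0.3 to 0.2 |

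All figures count evaluable participants.

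**The case against.** The strongest reply is that there is no contradiction. Section 10.7 names 11.4.5 as its source and calls the item an interim analysis, so it can be read as a short form of the rule in 11.4.5, with which 3.1, 11.2 and the Synopsis agree. That stands. A reader might infer that 10.7 and 11.4.5 command opposite actions, but the documents support only event-style wording plus silence on the case that matters.

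Second, a Simon design with its look at n1 is standard and need not be curtailed. The stated properties reproduce, so 11.4.5 is not a statistical error. That also stands.

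Third, the go/no-go rule is not the only purpose. Sections 11.4.1 to 11.4.3 plan a crPOPF rate with an exact interval, an SAE rate, an any-POPF rate and matched comparisons. Stopping near participant 13 would weaken all of them. This is a real cost, but it falls in a trial that has already failed its rule.

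Fourth, Section 3.3 allows termination for lack of efficacy and Section 12.1 lets the DSMC suspend the study. Those powers are discretionary. They permit a halt but do not say that one happens.

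**Conclusion.** The point holds as an ambiguity with a gap, and closing it is a cheap improvement worth making. Waiting for all 25 costs, at a true rate of 11.2%, 9.5 participants on average as an upper bound, about 7 to 8 with a lag of 2 to 3 participants, and about 4 to 5 if the full NSQIP lag applies. The last case is pessimistic, because chart review is allowed for the interim. If the treatment works as planned (2%), the difference is below one participant. These figures assume constant accrual and independent outcomes.

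Two stronger readings are not supported:
- A saving of about 11 participants (E[N] of 19.0) is reached only by also stopping at a third event in stage 2. Neither 10.7 nor 11.4.5 raises that, so it is an optional extension and no part of the inconsistency.
- The timing does not affect the error rates. The exact one-sided type I error is 0.058 whether the trial waits or halts. That this exceeds the Synopsis figure ("with a one-sided alpha level of 0.05") is a separate matter.

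**What to change.** Reconcile 10.7, 11.4.5 and 3.1, with the operative rule in 11.4.5:
- New injections halt once a second crPOPF is confirmed among stage 1 evaluable participants. Confirmation uses the chart review that 13.1.2.1 already allows; name who confirms and how discrepancies are settled.
- State that a confirmed crPOPF counts when it is confirmed, without waiting for that participant's day 30.
- Keep the look at 25 completed participants for the decision to continue.
- Make 10.7 and 3.1 refer to this rule in the same terms.
- In 11.2, restate the expected sample size under the null: 20.8 with immediate outcomes, or 22.3-23.1 with a lag of 2 to 3 participants. Power and type I error are unaffected.
- In 11.4.1, say how the crPOPF estimate and its interval reflect the curtailed sampling.

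The cost is a wording amendment and, if stage 1 fails, fewer participants for the crPOPF, SAE and matched estimates.

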### 11.5 HANDLING OF MISSING DATA

Every attempt will be made to obtain data at the defined time points as described in the primary and secondary endpoints. If the data are not sufficient to analyze specific endpoints, the participant's data may be excluded entirely or partially. No missing value imputation will be performed.

## 12. CLINICAL MONITORING

## **12.1 OHSU KNIGHT CANCER INSTITUTE DATA & SAFETY MONITORING PLAN**

All clinical trials at the Knight are required to have Data and Safety Monitoring Plan (DSMP). This study is under the oversight of the Knight Cancer Institute's DSMC as described in the Knight institutional DSMP. The Knight DSMP outlines the elements required to ensure the safety of clinical trial participants, the accuracy and integrity of the data, and the appropriate modification of cancer-related clinical trials for which significant benefits or risks have been discovered or when the clinical trial cannot be successfully concluded. The Knight DSMP also describes the methods and procedures for ensuring adequate, risk-based oversight of cancer-related research at OHSU.

As described in the Knight DSMP, regardless of a trial's risk level and any specific Knight oversight in place, the Investigator is singularly responsible for overseeing every aspect of the design, conduct, and final analysis of his/her investigation.

The Knight DSMC reviews and monitors study progress, toxicity, safety, and other data for this study. The DSMC will address any issue that raises questions about data integrity or trial participant safety with the Investigator and study team. Should any major concern arise, the Knight DSMC may recommend corrective action, and determine whether to suspend or terminate the study.

## **12.2 CLINICAL DATA & SAFETY MONITORING**

As part of the Quality Assurance plan and in full agreement with NIH policy (NIH Guide, NIH Policy for Data and Safety Monitoring, June 10, 1998) that states all clinical trials require monitoring to ensure the safety of study participants and the validity and integrity of the data, monitoring will be a continuous, ongoing and multifaceted process. This includes external review by the DSMC and IRB(s), as well as internal data quality control, review and evaluation. Site monitoring visits are central to this process, and will include reporting to appropriate individuals with oversight responsibilities.

The OHSU Investigator is ultimately, singularly responsible for overseeing every aspect of the investigation, including design, governing conduct at all sub-sites, and final analysis of study data.

In the absence of a formal monitoring plan, the Investigator may work with his/her study team to conduct and document internal monitoring of the study to verify protection of human participants, quality of data, and/or ongoing compliance with the protocol and applicable regulatory requirements.

If at any time Investigator noncompliance is discovered at OHSU or any sub-site, the Investigator shall promptly either secure compliance or end the Investigator's participation in the study.

Independent audits will be conducted by the Knight DSMC to verify that the rights and well-being of human participants are protected, that the reported trial data are accurate, that the conduct of the trial is in compliance with the protocol and applicable regulatory requirements, and that evidence of ongoing investigator oversight is present.

## **12.3 QUALITY ASSURANCE & QUALITY CONTROL**

The investigational site will provide direct access to all trial related source data/documents, and reports for the purpose of monitoring by the monitor and/or sponsor, and auditing by the Knight DSMC and/or regulatory authorities.

All clinical trials at the Knight Cancer Institute are required to have a Data and Safety Monitoring Plan (DSMP). All clinical work conducted under this protocol is subject to ICH GCP guidelines. This includes inspection of study-related records by the lead site, Sponsor, its designee, or health authority representatives at any time.

QA audit activities will occur as detailed in the Knight's institutional DSMP. All discrepancies, queries, deviations, observations, and findings of non-compliance will be compiled into a final audit report. The PI must review and assess each finding, and generate a response to the audit report that incorporates Corrective and Preventative Action (CAPA). A CAPA must approach analyzes root cause(s) of noncompliance in order to identify and determine changes to correct and resolve issues, and prevent recurrence.

Quality Control (QC) activities will occur to monitor and ensure the safety of study participants and the validity and integrity of data. Monitoring will be a continuous, ongoing and multifaceted process. This includes review by the Knight DSMC and applicable IRB(s), as well as internal data quality control, review and evaluation. Site monitoring visits are central to this process, and will include reporting to appropriate individuals with oversight responsibilities.

The Sponsor-Investigator, or study monitor, will verify that the clinical trial is conducted and data are generated, documented (recorded), and reported in compliance with the protocol, GCP, and the applicable regulatory requirements (e.g., Good Laboratory Practices (GLP), Good Manufacturing Practices (GMP)).

